1.11 Anti-tumor Lymphocyte Cytotoxicity Assay (Cytotoxicity Assay)

Functional tolerance may further be investigated by autologous tumor cell cytotoxicity assays. Functional video microscopy, such as Essen Bioscience's IncuCyte Zoom® Live Cell Analysis System may be used in these assays.

1.12 COVID-19 Research

The rationale for amending the protocol to expand the aim of immunology research into COVID-19 was made due to the clinical and scientific expertise of the Principal Investigator and his scientific team, the study site's apheresis equipment and clinical lab infrastructure, and lastly *BioCytics'* research lab infrastructure; all of which could be directly applied to viral immunology research, potentially benefitting the COVID-19 pandemic crisis. The expansion aim was first drafted to include healthy adult volunteers convalescing from COVID-19 to acquire PBMCs and plasma from these individuals to aid in the discovery of a vaccine or monoclonal antibody treatment against SARS-CoV-2 (the pandemic viral pathogen responsible for COVID-19 disease). This amendment was made possible via the Letter of Amendment (LoA) version 1-Apr-2020, IRB approved on 24-Apr-2020. The second revision for COVID-19 research occurred through a revised LoA version 16-Sep-2020, IRB approved 09-Oct-2020. The second revision was amended to primarily to incorporate SARS-CoV-2 diagnostic testing via the collection of biospecimen samples from nasal, nasopharyngeal (NP) and oropharyngeal (OP) swabs and microcapillary sampling in both children (5-17 years of age) and adults with suspected or confirmed COVID-19 with the purpose of supporting EUA device kit or test validations.

To create an ease of interpretation at the study site(s), the two IRB approved Letter of Amendments for COVID-19 research, version 1-Apr-2020 and version 16-Sep-2020 respectively, will be fully incorporated into this protocol as pertinent. Thus, this protocol amendment version 09-Dec-2020, will supersede LoA version 16-Sep-2020, enabling all aspects of this research study to be carried out under this protocol.

The aim of COVID-19 research in this protocol is intended to be applicable to other viral pathogens capable of pandemics and not limited to SARS-CoV-2. However, currently the protocol is meant specifically for COVID-19 related research and any change will require further clarification and/or amendment and submission to the IRB for approval.

Version Date: 8-Dec-2020

Confidential 15 | Page

2. STUDY DESIGN

This is an observational prospective laboratory biospecimen collection and device/platform development protocol to collect data for future device/platform submission for "device/platform approval" by the FDA. There may be other applications that are discovered with the use of this device or through biospecimen collection. This study also serves as the means to function as a biobank to support future scientific investigation across a multitude of fields outside of cancer immunotherapy, such as regenerative medicine, cell therapy development for autoimmune and inflammatory disorders, and for vaccine or therapeutic discovery for infectious viral pathogens of pandemic nature.

2.1. Objectives

2.1.1 Primary Objective

This is a study to investigate the feasibility of harvesting, expanding, and selecting T lymphocytes from cancer patients and healthy volunteers. The preliminary objective of this study is aimed at selecting PD-1⁺ and CTLA4⁺ T cells and other cellular fractions from peripheral blood of cancer patients and healthy volunteers by using specific conjugated antibodies, evaluating their functional *ex vivo* anti-tumor cytotoxicity against targeted autologous tumor cells.

2.1.2 Secondary Objectives

- Develop methodology and proprietary techniques towards collecting and expanding viable circulating tumor cells and immune cells collected through leukapheresis/apheresis.
- Develop methodology and proprietary techniques towards using viable circulating tumor cells and immune cells for tumor apoptosis-viability assay (TAVA) after exposure to chemotherapy and immunotherapy targeted drugs ex vivo, and lymphocyte tumor cytotoxicity assays.
- Optimize rapid expansion protocol for PD-1+ T cells, and other leukapheresis derived cell fractions.
- Upon validation of BioCytics circulating tumor cell TAVA, and lymphocyte tumor cytotoxicity assay, an FDA Pre-market Notification 510(k) application for in vitro device platform will be submitted.
- An FDA Investigational New Drug (IND) application for Lymphocyte T cell immunotherapy platform will be submitted.
- Continued assessment of bioinformatics, cell processing, genomic, and cryogenic infrastructure needed to create a biobank for tumor cells, immune cells, and hematopoietic stem and progenitor cells.
- Banking and sourcing of plasma, tumor cells, and immune cells from peripheral blood for facilitation of biomarker discovery.

Version Date: 8-Dec-2020

Confidential 16 | Page

- Develop methodology for isolation, selection, enrichment, and expansion of immune suppressor cell fractions, such as Tregs and MDSCs, for the advancement of therapeutic cell therapy of autoimmune and inflammatory disorders.
- Develop preliminary methodology for isolation, selection and cryopreservation of hematopoietic stem and progenitor cells from apheresis without mobilization.
- PBMC and plasma isolation from whole blood and apheresis of convalesced COVID-19 subjects for biobanking.

2.2 Endpoints

2.2.1 Primary Endpoint

Successful selection of PD-1⁺ and CTLA4⁺ T cell, and other immune cellular fractions from peripheral blood or leukapheresis of study subjects by using antibody conjugation, and evaluation of functional *ex vivo* anti-tumor cytotoxicity against targeted autologous tumor cells.

2.2.2 Secondary Endpoint

Prove hypothesis that selected and expanded PD-1* and CTLA-4* T cells, and/or other cellular fractions, have higher anti-tumor cytotoxicity than un-selected T cells from either patient peripheral whole blood or leukapheresis product.

Use this proof of principal, to then optimize a model platform for *ex vivo* T cell expansion towards an FDA IND submission for human applications on a clinical trial, *BioCytics'* Protocol #0002.

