5. STATISTICAL METHODS

5.1. Sample Size Determination

An approximate of 1500 cancer patients and/or healthy volunteers are to be enrolled in this study. The sample size is not determined from a power analysis and may be incremented based on the Principal Investigator's discretion and upon IRB/IEC approval.

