5.2. Statistical Consideration

The study is not powered for prospective statistical significance, however retrospective statistical tests may be applied to determine preliminary trends between tumor viability/apoptosis assays (TAVA), lymphocyte tumor cytotoxicity assay (LTCA), CTC enumeration, phenotyping, lymphocyte flow cytometry, and clinical tumor responses.

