5.3. Statistical Analysis

All data will be listed individually by study subject. For quantitative parameters, summaries for descriptive statistics will include the mean, standard deviation, minimum, median, and maximum. For qualitative parameters, summaries for descriptive statistics will include the frequency and percentage.

6. VALIDATION OF TUMOR APOPTOSIS-VIABILITY ASSAY (TAVA) AND LYMPHOCYTE TUMOR CYTOTOXICITY ASSAYS (LTCA)

Validation of *BioCytics'* TAVA and (LTCA) will be compared to other tumor profiling assays that may have already been performed as clinical standard of care (such as Foundation One, Caris, ImmunoSeq).

Apoptosis is characterized by loss of membrane integrity and the appearance of "membrane blebs" due to the ballooning appearance of the cell membrane. These morphological changes can be monitored using time-lapse video microscopy. As an alternative validation approach, we will confirm our TAVA & LTCA results by examining morphological features of apoptosis.

Results from the TAVA & LTCA may be reported to the treating oncologist for research purposes only. These research results will not affect or change standard of care or treating regimens established by the National Comprehensive Cancer Network (NCCN) guidelines.

Version Date: 8-Dec-2020

Confidential 38 | Page

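### Section 2.2.2 promises proof that selected cells are more cytotoxic than un-selected T cells, but Section 5 gives no confirmatory basis for that claim and plans no comparison

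*Protocol*

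**What the plan says.** Protocol 2.2.2 (Secondary Endpoint) opens with the words "Prove hypothesis that selected and expanded". The cells meant are those selected for PD-1 and CTLA-4, and the scope is widened by the phrase "and/or other cellular fractions". The claim to be shown is that these cells kill tumor better than T cells that were not selected, whichever of the two blood sources is used. The next paragraph gives the result a use: "Use this proof of principal, to then optimize a model platform", with an IND submission as the goal.

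Section 5 says the following.

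- 5.1: enrolment is put at about 1,500, patients and volunteers together. On its basis the section says: "The sample size is not determined from a power analysis and may be incremented based on the Principal Investigator's discretion". An increase also needs IRB/IEC approval, under both this section and 2.3.1.
- 5.2: "The study is not powered for prospective statistical significance". Tests done after the fact are allowed as an option, to look for early trends among the apoptosis and cytotoxicity assays, circulating tumor cell counts, phenotype and flow cytometry data, and tumor response. Selected versus un-selected cells is not named as a contrast.
- 5.3: data are listed by subject. The numeric measures get a standard set of statistics: "summaries for descriptive statistics will include the mean, standard deviation, minimum, median, and maximum". Categorical measures get counts and percentages. No between-product comparison or confidence interval is given, and nothing is said about pairing.

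**The concern.** Section 2.2.2 states a directional, comparative hypothesis and makes a development step depend on it. That is confirmatory language. Section 5 describes an exploratory study with descriptive output. A team following both sections could declare the endpoint proved by setting one mean beside another, with no estimate of the difference, no measure of its uncertainty and no rule for what counts as success. The opening to other cell fractions makes this looser, because the number of comparisons that could supply the proof is not fixed.

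The form of the summary also matters. The primary endpoint (2.2.1) uses autologous tumor cells as targets, so the natural comparison is within a donor: selected and un-selected cells against the same tumor. Separate means and SDs do not show how variable that within-donor difference is.

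**Working it through.** **1. Is there a figure to reproduce?** No. The enrolment of about 1,500 is expressly not derived from a power analysis, and no alpha, effect size or SD is given. This is not an arithmetic error. Nor is 1,500 the number of donors for this contrast: by 2.3.1 it includes healthy volunteers and children limited to swabs, microcapillary samples, saliva or urine.

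**2. The two positions side by side.**

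| Question | Section 2.2.2 | Section 5 |
|---|---|---|
| Aim | proof of a directional difference | preliminary trends (5.2) |
| Contrast | selected versus un-selected | not named (5.2, 5.3) |
| Inference | implied by proof | optional and retrospective (5.2) |
| Planned output | none stated | listings and descriptive summaries (5.3) |
| Power | none stated | disclaimed (5.1, 5.2) |

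An SAP that added a confirmatory test would depart from 5.2. An SAP that followed 5.2 could not support the word proof in 2.2.2. The protocol text has to change in either case.

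**3. What pairing is worth.** Assumptions, none from the protocol: *n* donors each give both products, common SD σ, within-donor correlation ρ of 0.5 to 0.8.

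- Standard error ignoring pairing: σ√(2/n)
- Standard error using pairing: σ√(2(1−ρ)/n)
- Ratio: 1/√(1−ρ)
- ρ = 0.5: 1/√0.5 = 1.41. ρ = 0.8: 1/√0.2 = 2.24.
- Equivalent number of donors is the ratio squared, 1/(1−ρ): 2 times at ρ = 0.5 and 5 times at ρ = 0.8.

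With complete pairs the difference of the two means is the same either way. What separate summaries lose is its standard error.

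**4. Is the comparison out of reach?** No. For a paired test at two-sided 0.05 with 80% power (assumed, normal approximation), pairs = ((1.960 + 0.842)/dz)², where dz is the mean difference divided by the SD of the differences.

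| dz (assumed) | 0.2 | 0.3 | 0.5 | 0.8 |
|---|---|---|---|---|
| pairs needed | 197 | 88 | 32 | 13 |

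The protocol does not say how many donors yield both products and an autologous target, so whether these numbers are available is unknown.

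**5. Further fractions.** If *k* fractions were each tested at 0.05 with independent results (assumed; the protocol sets no such test), the chance of at least one false positive is 1 − 0.95^k: 9.8% for 2, 14.3% for 3 and 22.6% for 5. Fractions from the same donors would probably be positively correlated, which would lower these figures. They show only why results for extra fractions should be labelled exploratory.

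**The case against.** The best defence is context. This is an observational biospecimen study with a feasibility objective (2.1.1), described in 3.2.2 as a pilot. Section 2.2.2 itself speaks of a proof of principle, Section 5 is candid about power, and no alpha or success test is claimed that could be inflated. Choice of test and handling of repeat collections commonly sit in an SAP. All of this is fair. It limits the seriousness of the point but does not remove it, because the conflict is between two statements in the protocol rather than a missing detail.

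It can also be argued that the cytotoxicity assay, phenotype and flow cytometry data named in 5.2 cover the contrast by implication. They might, but only as optional trend-seeking, which is still not proof.

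Four stronger readings are tempting, and the protocol does not support them.

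- *That 5.3 prescribes an unpaired analysis.* It is silent on pairing, and listing by subject keeps the pairs identifiable. A within-donor difference could itself be a summarised parameter.
- *That the sample size can be extended at the investigator's discretion alone.* IRB/IEC approval is also required (5.1, 2.3.1). Such approval does not control type I error, but it is part of the rule.
- *That the hypothesis will be tested repeatedly as donors accrue.* No section sets repeated looks or ties an extension to cytotoxicity results, so no inflated error rate can be attributed to the plan on that ground.
- *That the comparison cannot be delivered.* Lack of a power calculation does not make it impossible; under assumed effects, modest numbers of pairs would do.

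**Conclusion.** The point holds as an internal inconsistency: the protocol sets no confirmatory basis for the proof that 2.2.2 promises, and Section 5 as written would let that proof be declared without any comparative analysis. This conclusion rests on the text alone.

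The numerical part is conditional. If the two products were reported only as separate means and SDs, the standard error of the difference would be 1.4 to 2.2 times the paired one, for an assumed correlation of 0.5 to 0.8 and equal variances. The protocol neither requires nor rules out that course. The inconsistency should be corrected, because it affects what the study may conclude and what is carried towards the IND, but it does not undermine the collection itself.

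**What to change.** In 2.2.2, replace the opening words up to and including *that* with *Estimate whether, and by how much,* and state that the result is exploratory.

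In 5.3, add one comparative summary: the mean within-donor difference in cytotoxicity (selected minus un-selected, same collection, same autologous target) with a 95% confidence interval. Count each donor once, or use a donor random effect where a donor has several collections. Label results for further cell fractions as exploratory. Finer assay and donor-set rules can be left to the SAP.

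The cost is wording in two sections, with no new samples or procedures. The stated claim becomes less strong: an estimate with its uncertainty in place of proof.

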2.3. Selection of Study Population

Study participants include adult cancer patients of all stages of solid tumor origin and healthy volunteers. Healthy volunteers may vary in nature and can be further classified based on different criteria, as best summarized in section 2.3.1. below and section 10.7 Appendix 7. Healthy volunteers' scope of participation is primarily due to whether the healthy volunteer is deemed by the Principal Investigator or treating physician as "truly healthy" with no clinically significant medical disease or disorder, or if the healthy volunteer is "otherwise healthy". The latter is due to the subject having a history of autoimmune disease, inflammatory disorder, or is suspected/diagnosed with COVID-19 disease yet is otherwise clinically stable.

Adult healthy volunteers that fall into this second category will be carefully assessed by the Principal Investigator or treating physician to assure subject safety and data integrity. Subject eligibility criteria will also be carefully assessed and organized accordingly as to what it is pertinent and/or necessary to fulfill. With respect to COVID-19 and its disease transmission, healthy volunteers may also include pediatric subjects, aged 5-17 if parental consent is granted and assent where applicable is obtained. Lastly, healthy volunteers may also include consented employees from either *BioCytics'* or the study site(s)'; however, most healthy volunteers are community-based individuals and not employees. Consented employees may mostly participate in whole blood collection for instrument or device validation purposes, yet due to the COVID-19

Version Date: 8-Dec-2020

Confidential 17 | Page

pandemic, employees who are suspected of or have been diagnosed with COVID-19 may wish to participate in collection of biospecimens for that aspect of this study.

2.3.1. Study Population & Sample Size

The number of study subjects to be enrolled in this prospective observational biospecimen collection laboratory research study is approximately 1,500. This target population may be increased if needed; however, proper notification and approval by the IRB/IEC (Institutional Review Board/Independent Ethics Committee) must occur.

The population of patients to be enrolled for this study will consist of two cohorts: 1) cancer patients, and to a lesser extent 2) healthy volunteers.

1) Cancer patients must have a solid tumor histological diagnosis and can be at any stage of disease progression, including in the pre-surgical/neoadjuvant setting, receiving adjuvant therapy, and those considered in remission. Most cancer patients are referred to the study site(s) by their treating oncologists; however, a portion are self-referrals.

Cancer patients receiving any form of treatment, including those participating in clinical trials with experimental study drugs, will be allowed to participate in this observational biospecimen laboratory study. While enrollment will be geared towards patients with histologically proven metastatic solid tumors, a portion of the subjects may be non-metastatic solid tumor cancer patients in the neo-adjuvant, adjuvant, and in remission settings.

Cancer patients in the earlier stages of disease progression serve to research the baseline status of a patient's immune system in their tumor prior to receiving any treatment, to attempt to culture tumor infiltrating lymphocyte (TILs), and lastly, to attempt to "filterout" or collect CTCs downstream of the leukapheresis procedure or upon peripheral whole blood collection. As referenced in section 1.3. of this protocol, collection/filtration and enumeration of CTCs may serve as a diagnostic companion and promising prognostic tool in the adjuvant setting.

2) Healthy volunteers make up the second, smaller study population for this observational biospecimen laboratory study. Healthy volunteers serve primarily to aid in the proficiency, quality control and/or optimization of study procedures, experimental design assay development, and for device/equipment validation. Most healthy volunteer adult subjects are referred to the study site(s) by community-based word of mouth, however a smaller portion of them may be employees of either the study site(s) or of BioCytics.

The classification criteria seen below, serve to aid study design and to help identify the component(s) a study subject may participate in at a given time point based on their eligibility criteria and the cohort they are in.

Version Date: 8-Dec-2020

Confidential 18 | Page

Classification Criteria for Healthy Volunteer Cohort:

- Subjects with no pre-existing medical conditions or disorders, deemed as "truly healthy" by the Principal Investigator or treating physician's discretion.
- Subjects with a history of autoimmune diseases and/or inflammatory disorders who are otherwise considered "healthy" by the Principal Investigator or treating physician's discretion.
- Subjects who are employees of the study site(s) and/or BioCytics
- Subjects who have been diagnosed with presumable or confirmed viral pandemic pathogens, including but not limited to SARS-CoV-2, either in the acute, sub-acute, and convalesced state, but who are otherwise considered "healthy" by the Principal Investigator or treating physician's discretion.
 - Children from 5-17 years of age may participate in this study based on specific minimally invasive biospecimen collection procedures (outlined below and in section 3.2.1. Procedures by Study Visit) and with appropriate parental consent, and child assent where possible.

Due to the COVID-19 pandemic and the consequent amendment to aid in the research response, study subjects with COVID-19 disease may participate in all aspects of this protocol, but depending on their disease state, infection timeline, and age, participation may be limited to only one component, procedure, and/or type of biospecimen collection. Age is a very important criteria, as pediatric subjects (5-17 years old) will only be eligible to participate in minimally invasive biospecimen collection procedures. These procedures will be limited to the collection of swabs (nasal, nasopharyngeal and/or oropharyngeal), microcapillary samples, and saliva or urine collection.

Healthy volunteers, including those with history of autoimmune diseases or inflammatory disorders may participate in collection of biospecimen samples, primarily through peripheral whole blood draws or leukapheresis, since these may be beneficial for future cell therapeutic indications utilizing enrichment and expansion assays of Tregs and MDSCs. Healthy volunteers who have no history of disease or medical condition may participate in leukapheresis for preliminary attempts at isolation, selection and cryopreservation assay development of hematopoietic stem and progenitor cells (HSPCs) without the use of mobilizing agents. Upon optimization of these techniques, a protocol specific for the mobilization of HSPCs to the peripheral circulation in healthy volunteers must be drafted and submitted for approval, as mobilizing a patient would require a separate clinical trial protocol.

Version Date: 8-Dec-2020

Confidential 19 | Page

2.3.2. Study Duration

The open enrollment period for the study is anticipated to be for at least 5 years from the time of approval or until 1500 study subjects have been enrolled. Once enrolled, study subjects will remain on the study to be followed for biospecimen collection. Study subjects will be followed until the study closes or a patient is discontinued due to screen-failure, withdrawal, or disease progression and death.

It is anticipated that cancer patients may remain on study throughout the natural history and progression of their disease. The study duration may overlap with multiple lines of anti-cancer therapy, and as long as patient performance status remains $ECOG \le 3$ for patients not undergoing leukapheresis and $ECOG \le 1$ for patients undergoing leukapheresis collection. Cancer patients' tumor status and survival data may be followed through communication with the clinic site for another 5 years after active enrollment has stopped.

Healthy volunteers and surviving cancer patients (those most likely in earlier stages of disease progression or considered in remission), will remain on the study until the study closes or the subject discontinues or withdraws consent. Healthy volunteers will not be followed up annually unless clinically indicated by the Principal Investigator or treating physician. Additionally, COVID-19 healthy volunteers may be discontinued prior to study closure if BioCytics 0003, a protocol specific for pandemic viral pathogens including SARS-CoV-2, is drafted and submitted for approval. In the event that IRB approval is obtained, adults with COVID-19 may be asked to either continue their participation in BioCytics 0001 as a healthy volunteer for other aspects of this protocol or be removed from the study altogether. These adult subjects may then be asked to continue their COVID-19 research participation via the new study protocol BioCytics 0003. However, all pediatric patients enrolled in BioCytics 0001 for COVID-19 research would be discontinued from this study upon implementation of protocol 0003. This is due to BioCytics 0001 having no indication for pediatric healthy volunteers outside the scope of COVID-19 research.

